#### 3.8.2 Identity of Investigational Products

#### 3.8.3 Storage and Handling Procedures

JTT-662 Tablets, 1 mg or 10 mg and Placebo Tablets should be stored between 20 - 25°C in a secure location with restricted access.

#### 3.8.4 Clinical Supplies Packaging

A sufficient quantity of JTT-662 Tablets, 1 mg or 10 mg and Placebo Tablets will be supplied by Akros or designee, to the site.

Bulk JTT-662 and Placebo Tablets are packaged in glass bottles with a low-density polyethylene cushioning material, two alumina/silica desiccant packs (1 g) and capped with a polypropylene screw cap fitted with a polypropylene/polyethylene liner. Each bottle contains 30 tablets of either JTT-662 (1 mg or 10 mg) or Placebo Tablets, and will be labeled appropriately. Each label will bear appropriate text as specified by regulatory requirements.

Glass bottles and closures will be provided by Akros or designee, to the pharmacy for subject-specific packaging of JTT-662 or Placebo Tablets. Each label will bear the appropriate text as specified by regulatory requirements.

Study drug should be packaged for subject administration on the day of dosing, however, if this is not feasible, the weekday dose may be packaged up to 24 hours prior to dosing. Weekend dosing may be packaged up to 72 hours in advance of dosing.

### 3.8.5 Administration of Study Drug and Metformin

On the morning of Day -1, all subjects will receive a single oral administration of placebo following an overnight fast (for at least 10 hours) and 30 minutes before the start of a standard breakfast. On the morning of Day 1, randomized subjects will receive oral QD administration of JTT-662 or placebo, for 28 days from Day 1 through Day 28 following an overnight fast (for at least 10 hours) and 30 minutes before the start of a standard breakfast. Standardized lunch and dinner will be provided at 4.5 and 10.5 hours, respectively, post-dose. Metformin should be administered with food as per the label.

Water will be restricted for 1 hour before and after study drug administration for all cohorts. The planned dose levels and the number of tablets to be administered are provided below:

Cohort	Study Treatment	Number of Tablets (Per Dose)
1	Day -1: Placebo single dose	Five tablets of placebo
	Day 1 through Day 28: JTT-662 5 mg (or placebo) QD	Five tablets of JTT-662 1 mg or five tablets of placebo
2	Day -1: Placebo single dose	One tablet of placebo
	Day 1 through Day 28: JTT-662 10 mg (or placebo) QD	One tablet of JTT-662 10 mg or one tablet of placebo
3*	Day -1: Placebo single dose	Two tablets of placebo
	Day 1 through Day 28: JTT-662 20 mg (or placebo) QD	Two tablets of JTT-662 10 mg or two tablets of placebo

^{*} Cohort 3 will be initiated only after a review of the safety, tolerability, PK (up to Day 29 for Cohort 2) and available PD data from Cohorts 1 and 2 by the Sponsor, the Medical Monitor and the Investigator.

Tablets will be administered with 240 mL of potable water, followed by a hand check, if applicable, and a mouth check. Subjects having difficulty swallowing the required number of tablets with 240 mL of water may receive additional, documented amount of water sufficient to complete drug administration. Only authorized members of the site will administer the study drug. Dosing times will be staggered between subjects for practical reasons. The time of dosing will be recorded for each subject.

All subjects should remain semi-recumbent for 2 hours after study drug administration except for non-supine assessments, breakfast and restroom visits.

#### 3.8.6 Management of Clinical Supplies

The Investigator will have responsibility for the control and proper administration of all study-related drugs (which includes any investigational product or interacting product) in accordance with this protocol. The Investigator at the site is responsible for ensuring that all study-related drugs will be stored at recommended storage temperatures, in a secured area, free of environmental extremes, with restricted access. The Investigator at the site also agrees that all study-related drugs will be dispensed only to study subjects who have provided written informed consent and have met all inclusion criteria and none of the exclusion criteria.

#### 3.8.7 Randomization

Approximately 36 healthy subjects will be randomized in this study in 3 planned cohorts. In each cohort, 12 subjects will be randomized to receive JTT-662 or placebo (9 active: 3 placebo) on Day 1.

The randomization code will be prepared by an unblinded statistician or designee using an in-house program written in SAS®, a computer software package. Alors or designee will provide the randomization code to the pharmacy at the site, as well as to select laboratories, as appropriate (see Section 3.8.8).

#### 3.8.8 Blinding

On the morning of Day -1, all subjects will receive a single oral dose of placebo in an unblinded manner. From the morning of Day 1 to the morning of Day 28, all randomized subjects will receive JTT-662 or placebo QD in a single-blind manner. JTT-662 and Placebo Tablets will be supplied as unbranded tablets which are identical in appearance.

The pharmacist at the site will be responsible for packaging and dispensing the study drug in order to maintain the blind. The treatment assigned to each subject will not be disclosed to the subject; however, the Investigator and site staff will be unblinded. The treatment codes will be controlled by the site's pharmacy or designee.

The laboratory performing the JTT-662, metabolite and metformin (if analyzed) plasma concentration assessments will be unblinded to facilitate analysis of all samples from the JTT-662-treated subjects and appropriate samples from the placebo-treated subjects (see Section 3.6.7.30).

### 3.8.9 Breaking the Blind

Not applicable.

#### 3.9 Statistical Methods

This section provides an abbreviated statistical analysis plan (SAP) for safety, PK, PD parameters. A formal SAP will be developed at a later time. Statistical issues not addressed in the present section may be developed in the formal SAP. Any deviations to the SAP will be discussed in the study report.

#### 3.9.1 Subject Populations for Analysis

Randomized Population: All subjects randomized to receive JTT-662 or placebo on Day 1.

**Safety Population**: All subjects who received at least one dose of JTT-662 or placebo, including those who do not complete the study.

**Pharmacokinetic Population**: All randomized subjects who received at least one dose of JTT-662 or placebo, and have evaluable JTT-662 plasma concentration data. Subjects will be excluded or partially excluded from the statistical analysis of PK parameters if they significantly violated the inclusion or exclusion criteria or deviated significantly from the protocol.

**Pharmacodynamic Population:** All randomized subjects who received at least one dose of JTT-662 or placebo, and have evaluable PD data to facilitate the calculation of PD parameters. Subjects will be excluded or partially excluded from the statistical analysis if they significantly violate the inclusion or exclusion criteria or deviated significantly from the protocol.

### 3.9.2 Sample Size

Approximately 36 subjects (3 cohorts, 12 subjects per cohort [9 active: 3 placebo]) will be randomized into this study. The sample size is not statistically determined.

#### 3.9.3 Interim Analysis

Interim analysis is not planned for this study.

### 3.9.4 Safety Analysis

All subjects in the safety population will be included in the safety data analysis.

The safety evaluation will include AEs, clinical safety laboratory tests (e.g., hematology, serum biochemistry, coagulation, urinalysis), vital signs, 12-lead ECGs, Bristol Stool Chart findings, ketone bodies, FPG, urinary calcium excretion from the time of dosing until the 24-hour time point (UCE₀₋₂₄), urinary sodium excretion from the time of dosing until the 24-hour time point (UNaE₀₋₂₄) and UGE₀₋₂₄.

Adverse events will be coded using the Medical Dictionary for Regulatory Activities and will be summarized by SOC and preferred term.

Observed values and change from baseline of vital signs, ECG parameters and clinical laboratory data will be presented in tabular form with arithmetic mean, standard deviation (SD), median, minimum and maximum, or in frequency tabulation form as appropriate. For the laboratory safety data, out of range values and clinically significantly abnormal values will be flagged in the data listings.

Observed values and change from baseline of ketone bodies,

FPG will be summarized by treatment and time point.

#### Urine Calcium, Sodium and Glucose

Urinary calcium excretion from the time of dosing until the 24-hour time point (UCE₀₋₂₄), UGE₀₋₂₄ and UNaE₀₋₂₄ will be computed for Days -1, 1, 14 and 28. Observed and change from baseline of total excreted amount within 24 hours will be summarized by treatment and day.

Statistical analysis for change from baseline in  $UGE_{0-24}$  will be performed using a mixed effect model with repeated measures (MMRM). The model will include fixed effects for treatment, day, treatment by day interaction and baseline value. The treatment difference of each JTT-662 dose group relative to placebo at the same day will be estimated, along with two-sided 90% and 95% CIs and p-values.

JTT-662

#### **Bristol Stool Chart**

Total number of stools and percent of stools at each stool type will be summarized by treatment. Post-treatment highest stool type score will be also derived for each subject, and number and percent of subjects by the highest stool type will be summarized by treatment.

Other safety parameters may be summarized as appropriate.

#### 3.9.5 Pharmacokinetic Analysis

Pharmacokinetic analysis will be performed on the PK population unless otherwise stated.

#### 3.9.5.1 Pharmacokinetic Parameters

The following PK parameters will be derived by non-compartmental analysis using Phoenix® WinNonlin® (Version 6.4 or higher) and/or SAS® (Version 9.4 or higher) as appropriate. Additional PK parameters may be calculated, as appropriate.

• JTT-662 in plasma: C_{max}, trough concentration during multiple dosing prior to next dose (Ctrough), tmax, AUCtau, Vz F, CL F, t1/2, t1/2(eff), accumulation ratio of maximum concentration (AR_{Cmax}) and accumulation ratio of area under the concentration-time curve during a dosing interval (AR_{AUCtau}), and accumulation ratio based on trough concentration (AR_{Ctrough}).

#### 3.9.5.2 Pharmacokinetic Data Analysis

Descriptive statistics will be performed for all subjects in the PK population. The plasma concentration data and the PK parameters will be summarized in terms of the number of subjects (n), arithmetic mean, SD, CV%, median, minimum and maximum by treatment and day. In addition, geometric mean will be reported for all PK parameters except t_{max}.

Dose proportionality of C_{max} and appropriate AUC values on Day 1 and Day 28 will be assessed for JTT-662. The relationship between each parameter and dose is written as a power function:

Parameter = 
$$A*dose^b$$
 (Equation 1)

Where "A" is a constant, "b" is the proportionality constant and "parameter" is the PK parameter of interest (e.g., C_{max} and AUC_{tau}). Each PK parameter will be plotted against dose. The exponent, b, will be estimated by performing linear regression of the (natural) log-transformed parameter on the log-dose, since taking logarithm on both sides of (Equation 1) gives the linear relationship, log parameter = a + b*log dose, where a = log(A). Therefore the exponent, b, is estimated by the slope of the resulting regression line. A value of b close to 1 indicates dose proportionality. Dose proportionality will be assessed descriptively by presenting the estimate of b, its standard error and the 90% CI.

[figure not shown]
#### 3.9.6 Pharmacodynamic Analysis

Area under the observed effect-time curve from the time of starting breakfast until the 4-hour time point (AUEC₀₋₄) will be calculated for PPG on Days -1, 1, 14 and 28.

Postprandial glucose (PPG) concentrations will be summarized by treatment group and time point in terms of the number of subjects, arithmetic and geometric means, standard deviation, CV%, median, minimum and maximum.

A linear mixed effect model including day as the fixed effect and subject as the random effect will be fitted on the natural logarithm of the PD parameter for each treatment group separately. The ratio of the geometric means (Day 1/Day -1, Day 14/Day -1 and Day 28/Day -1) of AUEC₀₋₄ and the 90% and 95% CIs of the GMR will be calculated.

Additionally, the change from baseline of AUEC₀₋₄ will be analyzed using the MMRM model. The model will include fixed effects for treatment, day, treatment by day interaction, subject as repeated measures and baseline value. The treatment differences between each JTT-662 dose group relative to placebo at the same day will be estimated, along with two-sided 90% and 95% confidence intervals (CIs) and p-values.

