3.3 Randomization and Treatment Assignments

In each cohort, 12 subjects will be randomized to receive JTT-662 or placebo (9 active: 3 placebo) on Day 1. The randomization code will be prepared by an unblinded statistician or designee using an in house program written in SAS[®], a computer software package.

Eligible subjects will be assigned to a treatment according to the list of subject randomization assignments.

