6.8 Pharmacodynamic Analysis

Observed values and change from baseline of PPG concentrations will be summarized by treatment group and time point in terms of the number of subjects, arithmetic mean, SD, CV%, median, minimum and maximum. Baseline for PPG concentrations will be the pre-dose (Hour 0) value of the PPG profile on each PPG collection day. Concentrations will be listed, mean and individual plots will also be presented.

The plasma glucose excursion defined as the maximum glucose value observed after breakfast (0-4 hours after breakfast) minus the pre-dose (Hour 0) value will also be summarized for observed values and change from baseline on Days -1, 1, 14 and 28. Day -1 will be baseline.

Area under the observed effect-time curve from the time of starting breakfast until the 4-hour time point (AUEC₀₋₄) will be calculated for PPG on Days -1, 1, 14 and 28 for the PD population. Observed values and change from baseline of AUEC₀₋₄ will be summarized descriptively. Baseline will be the corresponding parameter value on Day -1.

A linear mixed effect model including day as the fixed effect and subject as the random effect will be fitted on the the PD parameter for each treatment group separately. The difference of the least square means of AUEC₀₋₄ between the compared days (Day 1 vs. Day -1, Day 14 vs. Day -1, Day 28 vs. Day -1 and Day 28 vs. Day 14) and the 90% and 95% CIs of the least square mean difference will be calculated.

The following sample SAS code may be used, with appropriate changes, for the analysis:

```
PROC MIXED DATA=DATASET;
BY TREATMENT:
  CLASS SUBJID DAY;
  MODEL PDPARVAL = DAY / DDFM=KR;
  RANDOM SUBJID;
  LSMEANS DAY / CL;
  ESTIMATE 'Day 1 Vs. Day -1' Day 1 0 0 -1/ALPHA = 0.05 CL;
  ESTIMATE 'Day 14 Vs. Day -1' Day 0 1 0 -1/ALPHA = 0.05 CL;
  ESTIMATE 'Day 28 Vs. Day -1 ' Day 0 0 1 -1/ALPHA = 0.05 CL;
  ESTIMATE 'Day 28 Vs. Day 14 'Day 0 -1 1 0/ALPHA = 0.05 CL;
  ESTIMATE 'Day 1 Vs. Day -1' Day 1 0 0 -1/ALPHA = 0.1 CL;
  ESTIMATE 'Day 14 Vs. Day -1' Day 0 1 0 -1/ALPHA = 0.1 CL;
  ESTIMATE 'Day 28 Vs. Day -1 ' Day 0 0 1 -1/ALPHA = 0.1 CL;
  ESTIMATE 'Day 28 Vs. Day 14 ' Day 0 -1 1 0/ALPHA = 0.1 CL;
 RUN;
```

[figure not shown]
Statistical Analysis Plan - Protocol No. AT662-U-20-003

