Additionally, the change from baseline (Day -1) of AUEC₀₋₄ will be analyzed using the mixed effect model with repeated measures (MMRM). The model will include fixed effects for treatment, day, and treatment by day interaction, subject as repeated measures and baseline value as a covariate. The difference of the least squares means between each JTT-662 dose group relative to placebo at the same day will be estimated, along with two-sided 90% and 95% CIs and p-values. Least squares means will also be presented.

[figure not shown]
The following sample SAS code may be used, with appropriate changes, for the analysis:

```
PROC MIXED DATA=DATASET;
 CLASS DAY TREATMENT;
 MODEL CHG = DAY TREATMENT DAY*TREATMENT BASELINE / DDFM=KR;
 REPEATED /SUBJECT=SUBJECT(TREATMENT) TYPE=UN*;
 LSMEANS DAY*TREATMENT /PDIFF CL ALPHA=0.1**;
RUN:
```

^{**} alpha = 0.05 and 0.1.

^{*} Other covariance structure will be used if UN leads to non-convergence of the model.

Statistical Analysis Plan - Protocol No. AT662-U-20-003

6.10 **Analysis of Safety Data**

Safety analyses will be conducted on the Safety Population and will be performed for all safety variables specified below.

The safety evaluation will include AEs, clinical safety laboratory tests (e.g., hematology, serum biochemistry, coagulation, urinalysis), vital signs, 12-lead ECGs, BSC findings, ketone bodies, urinary calcium excretion from the time of dosing until the 24-hour time point (UCE₀₋₂₄) and urinary sodium excretion from the time of dosing until the 24-hour time point (UNa E_{0-24}) and UGE $_{0-24}$.

Observed and change from baseline of vital signs, ECG parameters and clinical laboratory data will be presented in tabular form with arithmetic mean, SD, median, minimum and maximum, or in frequency tabulation form as appropriate. For the laboratory safety data, out of range values and PCS abnormalities will be flagged in the data listings.

Potentially clinically significant abnormalities will be defined according to the Akros Safety Reporting Standards Potentially clinically significant values for vital signs, ECG, and laboratory data will be flagged in data listings.

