6.10.6 Other Safety Data

Observed values and change from baseline of ketone bodies will be summarized by treatment group and time point.

Listing with subjects impacted by COVID-19 will be presented. Also, eGFR values will be listed.

Urine Calcium, Glucose and Sodium

The UCE₀₋₂₄, UGE₀₋₂₄ and UNaE₀₋₂₄ will be computed for Days -1, 1, 14 and 28. Observed values and change from baseline (Day -1) of total excreted amount within 24 hours will be summarized by treatment group and day. Descriptive statistics for 24-hour urine volume and fluid intake on Days -1, 1, 14 and 28 will be also presented for observed values and change from baseline.

Statistical analysis for change from baseline in UGE_{0-24} in the original scale will be performed using MMRM similar to that for PPG AUEC₀₋₂₄.

Bristol Stool Chart

Total number of stools and percent of stools at each stool type will be summarized by treatment group. Post-treatment highest stool type score will be also derived for each subject, and number and percent of subjects by the highest stool type will be summarized by treatment group and overall. A plot will be created for individual assessments over time.

Other safety parameters may be summarized as appropriate.

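### Minor, cheap improvement: the AUEC0-4 and UGE0-24 MMRMs impose one baseline slope on Days 1, 14 and 28; a baseline-by-day term would protect the Day 28 contrast if correlation with Day -1 decays

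*Protocol*

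**What the plan says.** Protocol 3.9.6 gives the AUEC0-4 model: "The model will include fixed effects for treatment, day, treatment by day interaction, subject as repeated measures and baseline value". Protocol 3.9.4, under urine calcium, sodium and glucose, gives the UGE0-24 model: "The model will include fixed effects for treatment, day, treatment by day interaction and baseline value". The SAP 6.8 sample code carries the baseline once: "MODEL CHG = DAY TREATMENT DAY*TREATMENT BASELINE / DDFM=KR". It uses an unstructured covariance with a fallback: "Other covariance structure will be used if UN leads to non-convergence of the model". SAP 6.10.6 says the UGE0-24 analysis "in the original scale will be performed using MMRM similar to that for PPG". The pointer there names AUEC0-24, but the only MMRM shown is the AUEC0-4 model in 6.8, so I read it as that form.

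The response is change from Day -1, and for AUEC0-4 "Baseline will be the corresponding parameter value on Day -1". The parameter "will be calculated for PPG on Days -1, 1, 14 and 28", so three post-baseline days are modelled. On group size: "In each cohort, 12 subjects will be randomized to receive JTT-662 or placebo (9 active: 3 placebo) on Day 1". SAP section 6 pools placebo over cohorts, so each dose contrast is 9 versus 9. SAP 6.8 asks for 90% and 95% CIs and p-values for each same-day contrast with placebo.

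**The concern.** When change from Day -1 is regressed on the Day -1 value, the slope at a given day depends on how strongly that day correlates with Day -1. Day 1 comes within two days of baseline; Day 28 comes after four weeks of dosing. If the correlation falls over that time, the true slopes differ. The model lets treatment effect and covariance vary freely by day but holds the slope fixed, and neither document says why.

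Under an unstructured covariance, generalised least squares takes the common slope mainly from the day with the least residual variance given baseline. With decaying correlation that is Day 1. The slope is then too shallow for Day 28. Part of any chance baseline difference between a dose group and placebo stays in the Day 28 contrast, and the contrast varies more than it needs to. With nine subjects per group, chance differences are not small.

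**Working it through.** The plan has no figure of its own to reproduce: the sample size is not statistically determined, and no SD or correlation is given. All correlations below are assumed. Outcomes are in units of the between-subject SD.

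**Slope on one day.** b_d = r_d × SD_d / SD_base − 1, where r_d is the correlation of day d with Day -1. With equal SDs, b_d = r_d − 1.

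**Common slope.** Let S be the residual covariance of the three days given baseline. The weights are w = S⁻¹1 / (1'S⁻¹1) and the common slope is β = Σ w_d b_d.

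**Loss at Day 28.** Large-sample variance inflation is 1 + (b_28 − β)² / S_28,28. A baseline difference D leaves an error of (b_28 − β) × D in the contrast. With 9 versus 9, the SD of a chance D is √(2/9) = 0.471.

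*Scenario A:* r = 0.85/0.65/0.55; post-baseline correlations 0.70 (Days 1, 14), 0.60 (Days 1, 28), 0.75 (Days 14, 28).
- b = −0.15, −0.35, −0.45. S_28,28 = 1 − 0.55² = 0.6975.
- Weights 0.730, 0.146, 0.124. β = 0.730(−0.15) + 0.146(−0.35) + 0.124(−0.45) = −0.216, against −0.45 at Day 28.
- Inflation 1 + 0.234²/0.6975 = 1.078. In simulation, after paying for the extra parameters, the variance ratio was 1.064, or √1.064 − 1 = 3% in SE.
- Shift for a one-SD chance difference: 0.234 × 0.471 = 0.110, against an SE of √(0.6975 × 2/9) = 0.394, so 0.28 SE.

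*Scenario B:* r = 0.90/0.60/0.50; post-baseline 0.65/0.55/0.75.
- b = −0.10, −0.40, −0.50. Weights 0.846, 0.077, 0.077. β = −0.154, against −0.50.
- Inflation 1 + 0.346²/0.75 = 1.160; simulated 1.123, or 6% in SE.
- Shift 0.346 × 0.471 = 0.163, against √(0.75 × 2/9) = 0.408, so 0.40 SE.

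*Equal correlations of 0.7:* simulated variance ratio 0.990, so the planned model is about 0.5% better in SE.

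**Separate simulation over a wider range.** Four groups of 9, complete normal data, SD 1 on each day, no treatment effect, unstructured REML, 4,000 trials per row. Entries are the empirical SD of the Day 28 contrast.

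| r at Days 1/14/28 | One slope | Slope by day | Ratio |
|---|---|---|---|
| 0.9/0.9/0.9 | 0.204 | 0.205 | 0.995 |
| 0.8/0.8/0.8 | 0.279 | 0.281 | 0.994 |
| 0.9/0.85/0.8 | 0.290 | 0.292 | 0.995 |
| 0.9/0.8/0.7 | 0.338 | 0.330 | 1.023 |
| 0.9/0.75/0.6 | 0.397 | 0.387 | 1.027 |
| 0.8/0.65/0.5 | 0.420 | 0.410 | 1.025 |
| 0.9/0.7/0.5 | 0.446 | 0.420 | 1.064 |
| 0.9/0.6/0.3 (extreme) | 0.509 | 0.462 | 1.102 |

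With one slope, the mean error at Day 28 lay between −0.009 and +0.013 SD (simulation error up to about 0.008). Coverage of the 95% CI was 0.945 to 0.954, using t quantiles in place of Kenward-Roger degrees of freedom.

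**Sensitivity to SD.** Keep scenario A but set the Day 28 SD to 1.2 times baseline. Then b_28 = 0.55 × 1.2 − 1 = −0.34, β = −0.197, S_28,28 = 1.44 × 0.6975 = 1.004, and inflation falls to 1 + 0.143²/1.004 = 1.020. At 0.8 times baseline, b_28 = −0.56, β = −0.284, S_28,28 = 0.64 × 0.6975 = 0.446, and inflation rises to 1 + 0.276²/0.446 = 1.171.

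**The case against.** A single baseline slope is a legitimate, prespecified and parsimonious adjustment for 36 subjects. The design also gives reasons to doubt steep decay. Subjects live in-house from Day -3, meals are identical on the four assessment days (Protocol 3.6.5.1), and metformin stays stable. Day 1 is also the first active dose for 27 of 36 subjects, so it need not be the day closest to baseline. SAP section 6 says there will be no formal inferential testing, no primary PD day is named, and no decision rule depends on the Day 28 contrast. The SAP code is a sample that allows changes.

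Most of this stands, and it makes the point minor. It does not remove the point: intervals and p-values are still to be reported, the term uses data already collected, and no text in either document provides for it.

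A reader might go further and infer that the Day 28 contrast is wrongly adjusted, or that it is less precise as a matter of fact. The documents support neither. The contrast is unbiased over randomization with nominal coverage; the error exists only conditional on a baseline imbalance. Loss of precision needs correlation decay, and four weeks between visits does not by itself show that.

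**Conclusion.** Minor. Both MMRMs force one baseline slope on three days, and the planned contrasts are valid on average. If correlation with Day -1 decays moderately to strongly, a one-SD chance baseline difference shifts the Day 28 contrast by about 0.3 to 0.4 SE in the two worked scenarios, and the SE is about 2 to 6% larger than needed (10% in the extreme case). With flat or slow decay there is no loss, or about a 0.5% gain, from the plan as written.

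These sizes rest on assumed correlations, complete normal data and, apart from the sensitivity check, equal SDs. Nothing was calculated specifically for UGE0-24; the same algebra applies, but its correlations and SDs are equally unknown. The no-bias result also assumes no baseline drift between cohorts. Cohort 3 starts later, and 6 of the 9 pooled placebo subjects come from Cohorts 1 and 2, so such drift would not average out as chance imbalance does.

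**What to change.** In SAP 6.8, and by reference in 6.10.6, use `MODEL CHG = DAY TREATMENT DAY*TREATMENT BASELINE BASELINE*DAY / DDFM=KR;` for both AUEC0-4 and UGE0-24. Keep LS means at the overall mean baseline. Same-day contrasts with placebo do not depend on that choice, because the slope varies by day and not by treatment.

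SAP section 7 already records one departure from the protocol's PD analysis, so this one can be listed beside it. Protocol 3.9.4 and 3.9.6 can be aligned at the next amendment; the change does not warrant an amendment of its own.

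The cost is two extra parameters and about 0.5% wider SE if the slopes are in fact equal. No new data are needed.
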